Second Survey in the ED: We will administer a second short survey at some time (approximately 1 hour) after the FIRST SURVEY. See SECOND SURVEY: NON-INTERVENTION GROUP. These second surveys in the non-intervention group have the same key primary and secondary outcome questions as in the INTERVENTION GROUP second surveys. SECOND SURVEY: NON-INTERVENTION GROUP.

NOTE: All of the above study procedures should be performed in patient waiting times and not interfere or disrupt patient care in any way.

- **Research Staff Informing of ED Providers when Participants will accept Covid vaccine**

At this time all of our EDs have the capability of administering COVID19 vaccines in some manner, and we expect that this will continue for at least the first 6 months of the trial. The last question in the SECOND SURVEY **in both arms** of the study is “Would you accept the Covid vaccine in the emergency department today if your doctor asked

you?" When a participant says they will accept the vaccine, the CRC or research staff will ask the patient if they can notify the patient's providers (nurse and/or physician) that they said they will accept the vaccine. They will also ask the patient if they (the CRC) can check to see if the patient receives the vaccine in the ED.

Other than this question and notification, research staff will not push that they get vaccinated.

- **Consent for 1- Month Follow Up Surveys for patients saying No to Vaccine in ED**

For all patients saying **no** to the question "*Would you accept the Covid vaccine in the emergency department today if your doctor asked you?*", research staff will ask if they can contact them and review their records in a month for follow up via full written consent. If patient says yes, then the CRC will get full **written** informed consent, including a separate HIPAA form, for review of their records and phone call. See FOLLOW UP Consent. Patients will not be compensated for participation. We will then ask Subjects for their best phone number(s) to reach them for a follow-up phone call. Sites will maintain a separate password protected database of subject IDs and follow up phone #s. Patients may agree to a phone call and not the EHR review, or vice versa. In those cases obtain the relevant consent, and note that they have accepted only one or the other.

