We will also ask for 1-month follow up in those subjects who said YES to accepting the Covid vaccine in the ED and did not get the vaccine in the ED. We will attempt to get full **written** informed consent for review of their records and phone call at 1 month in the same manner as above.

- **Community Covid Vaccine Information for patients saying No to Vaccine in ED**

Additionally, if the patient says no to accepting the vaccine in the ED today, the CRC will also ask, "*Would you like some information about where you can get a Covid vaccine outside of the emergency department?*" If the patient says yes, then the CRC will provide information about where they can get a Covid vaccine outside of the ED (community locations).

- **Primary Outcomes and Ascertainment**

Our primary outcome for Specific Aim III is **vaccine acceptance at the time of SECOND SURVEY** (the converse of vaccine hesitancy) defined as a response of "yes" to the question "*Would you accept the Covid vaccine in the emergency department today if your doctor asked you?*" This and other outcomes for Specific Aim III will be ascertained during the SECOND SURVEYS at the end of their index ED visit. **If the patient says yes, the CRC will then ask the patient if it is acceptable for them to notify the provider and confirm their receipt of the vaccine.** If the patient says yes, the CRC will notify the provider that they are willing to get the vaccine. CRCs will later confirm with the provider that the patient received the COVID-19 vaccine in the ED.

Our primary outcome for specific aim IV will be **uptake (receipt) of a COVID-19**

vaccine (at any vaccination location) within 28 to 32 days after their index ED visit. For ascertainment of this primary outcome:

- As above, for patients who stated they would accept it in the ED today, CRCs will confirm whether the patient received the vaccine directly from providers or by review of that patient's EHR the following day.
- For those who do not accept the vaccine in the ED **and consent to follow up:** We will conduct EHR review and follow-up phone calls (*Have you received a COVID-19 vaccine?*) one month after index ED visits.

- **28 to 32 Day Follow-Up for Ascertainment of Primary Outcomes**

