CRCs will review Master Data Flow daily (workdays) to determine which subjects have reached the 28-day follow-up time period. The CRC will conduct the first follow-up EHR review and, if necessary, follow up phone call attempt on that 28th index day. For the subsequent second and third EHR reviews and follow-up phone calls, CRCs will use the following weekday calendar, which will ensure no greater than 32 days between the index visit and final outcome ascertainment:

Index Study Visit Day of Week	First Call (Same day of week as index study visit – 4 weeks later)	Second Call	Third Call
Monday	Monday	Tuesday	Wednesday
Tuesday	Tuesday	Wednesday	Thursday
Wednesday	Wednesday	Thursday	Friday
Thursday	Thursday	Friday	Monday
Friday	Friday	Monday	Tuesday

Study subject's medical record #s and telephone #s will be accessed from the **PROCOVAXED Follow up sheet. The CRC who conducts this EHR and phone follow-up will be blinded to the subject's study group assignment (intervention vs non-intervention), i.e., a separate CRC who does not recruit at that site will conduct this phone follow-up.**

- The CRC will first review the EHR to determine whether there is any record of a Covid vaccination in the preceding time period from the study index visit. If there is a record of vaccination, the CRC will record what date and where the study received it. See **Follow up Data Collection** form.
- If there is no record of vaccination in the EHR, the CRC will proceed with a phone call to the study subject. See **Follow up Data Collection** form. CRCs will enter follow up data on both the Master Data Flow and Follow up spreadsheets

via REDCap links.

- If the patient does not answer the phone that morning, the CRC will place two more calls to the study subject over the next 2 workdays. They will vary the time of these calls to improve response.
- If the patient does not answer the phone by the third call, the CRC will leave a message with the phone # of the study team. No more calls will be initiated by the study team after this third call.
- If there is no call received from the study subject one week after the 3rd call, the phone follow up will be considered as incomplete.

Of note, CRCs will only review EHR and conduct phone follow-up with study subjects who have given written consent for these follow-up techniques.

In terms of final ascertainment of Specific Aim 4 (uptake of Covid Vaccine within 28 to 32 days of index ED visit), we will use the following scheme:

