	Any of the following:
Yes, Covid vaccine received	
• Confirmed receipt of Covid vaccine during index ED visit• Confirmed receipt of Covid vaccine via EHR review• Confirmed receipt of Covid vaccine via phone follow-up call

	
All of the following:
 
 • Did not receive Covid vaccine in ED during index visit • Did not receive Covid vaccine on EHR review • Did not receive Covid vaccine on phone follow-up call 
No, Covid vaccine not received
 
**If subject did not receive Covid vaccine in the ED, these 2 scenarios will also qualify as Covid vaccine not received:
 
 • Did not received Covid vaccine on EHR review but unable to complete phone follow-up • Did not received Covid vaccine on phone follow-up but unable to complete EHR review
Indeterminate	Unable to review EHR and Unable to contact subject via phone call

- **Data Recording and Entry**

CRCs will record survey responses and other data via two mechanisms:

- Direct entry into the PROCOVAXED Study REDCap database in real time during surveys via secure links
- Recording onto paper forms first. Then entry of survey information and data after each participant enrollment.

CRCs will keep a running log of all study flow and enrollment, recording on REDCap forms the following data for all patients approached: study date, study arm, “Yes” and “No” to having received a Covid vaccine, “Yes” and “No” agreeing to first surveys, delivery or non-receipt of messaging platforms, agreeing to receipt of study vaccines, receipt of vaccines in the ED, “Yes” and “No” agreeing to follow-up calls and EHR review. See Enrollment Log and Master Data Flow. CRCs will also record First and Second Survey responses on REDCap. Sites are allowed to use either one of two methods for REDCap data entry: recording of survey response on printed sheets and later entering on REDCap, or recording responses in real time directly on REDCap via iPads.

- **Data Analysis**
- **Primary Analysis**

We will compare primary outcomes in patients seen on PROCOVAXED intervention dates with those seen on non-intervention dates to test our 2 study hypotheses. We will measure outcomes in all ED patients surveyed as our group of primary outcome

analysis.

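### Patients who say YES are asked for written follow-up consent only if they were not vaccinated in the ED, so some who leave undosed may have no obtainable Aim IV outcome

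*Combined protocol and SAP*

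**What the plan says.** - **Patients who say NO (Section XII).** The answer itself triggers the request: "research staff will ask if they can contact them and review their records in a month for follow up via full written consent". A separate HIPAA form goes with it.
- **Patients who say YES (end of Section XII).** The plan includes "1-month follow up in those subjects who said YES to accepting the Covid vaccine in the ED and did not get the vaccine" during the visit. The team will attempt to get written "informed consent for review of their records and phone call at 1 month in the same manner as above". No time point is given, and no remote or deferred way of signing.
- **Learning whether a YES patient was dosed (Section XIV).** "CRCs will confirm whether the patient received the vaccine directly from providers or by review of that patient's EHR the following day". Section XI describes only a verbal request to the patient for permission to check this.
- **Month-1 ascertainment (Section XIV).** The second bullet names only those who did not accept the vaccine in the ED and who consented to follow-up.
- **Limit on month-1 methods (28 to 32 Day Follow-Up).** "CRCs will only review EHR and conduct phone follow-up with study subjects who have given written consent for these follow-up techniques".
- **Outcome class.** The Indeterminate category is "Unable to review EHR and Unable to contact subject via phone call". No rule for analysing it is given.
- **Analysis set (Data Analysis, Primary Analysis).** "We will measure outcomes in all ED patients surveyed as our group of primary outcome" analysis.

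**The concern.** For NO patients, consent depends on nothing that happens later. For YES patients it depends on an event that follows the survey, and one of the two permitted ways of learning about that event comes a day later, when many patients will have gone home. Unless someone returns to the bedside in time, there is no signature, and without a signature there is no month-1 record review or call.

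Aim IV counts a dose received at any location. A patient who accepts, leaves undosed and is vaccinated in the community during the month is a success that the trial could fail to record. Undosed acceptors are foreseeable: Section XI expects ED vaccine capability for at least the first 6 months, while Sample Size Considerations projects about 50 weeks of enrolment. Outcomes that nobody had consent to collect cannot be recovered at the analysis stage.

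**Working it through.** **1. The plan's own figure.** Inputs from Sample Size Considerations: 15% vs 22%, alpha 0.05 (taken as two-sided), power 0.9.

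n per arm = [1.960·√(2·0.185·0.815) + 1.2816·√(0.15·0.85 + 0.22·0.78)]² / 0.07² = (1.0763 + 0.7009)² / 0.0049 = 644.6, so 645 per arm and 1,290 in total. This matches the plan. The figure contains no allowance for missing Aim IV outcomes.

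**2. The two consent paths side by side.**

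| Step | NO patient | YES patient |
|---|---|---|
| Trigger for written consent | the answer | the answer plus no ED dose |
| When the trigger is known | at the second survey | later: from the provider, or from the EHR next day |
| If the patient leaves first | not at issue | no signature, unless obtained some other way |
| Month-1 review or call without a signature | not permitted | not permitted |

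**3. How many patients are exposed.** YES answers: 645 × 0.15 = 96.75 (control) and 645 × 0.22 = 141.9 (intervention). The share u of YES patients not dosed in the ED is not in the documents. Assuming it is equal in the two arms:

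| u | Control | Intervention |
|---|---|---|
| 20% | 19 | 28 |
| 40% | 39 | 57 |
| 60% | 58 | 85 |

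These are upper bounds on the loss, reached only if no undosed YES patient is consented. The ordering of the arms also depends on equal ED delivery. If control delivers to 50% of acceptors, the two undosed groups are equal when 0.22 × (1 − v) = 0.15 × 0.5, that is v = 0.66. Above that delivery rate in the intervention arm, control has more.

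**4. Effect on the Aim IV difference.** All rates here except p are assumptions. Let p be the proportion saying YES, L the later uptake in undosed YES patients, b = 5% the later uptake in NO patients, k the share of undosed YES patients with no month-1 outcome, and m the same share for NO patients.

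True uptake = p(1−u) + p·u·L + (1−p)·b

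Complete-case uptake = [p(1−u) + p·u·(1−k)·L + (1−p)(1−m)·b] / [1 − p·u·k − (1−p)·m]

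Worked case, u = 0.4, L = 0.5, k = 1, m = 0:
- True: control 0.0900 + 0.0300 + 0.0425 = 0.1625; intervention 0.1320 + 0.0440 + 0.0390 = 0.2150; difference 5.25 points.
- Complete case: 0.1325/0.940 = 0.1410 and 0.1710/0.912 = 0.1875; difference 4.65 points.

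| u | L | k | m | Missing, control vs intervention | True difference | Complete-case difference |
|---|---|---|---|---|---|---|
| 0.2 | 0.50 | 1 | 0 | 3.0% vs 4.4% | 5.95 | 5.74 |
| 0.4 | 0.50 | 1 | 0 | 6.0% vs 8.8% | 5.25 | 4.65 |
| 0.6 | 0.50 | 1 | 0 | 9.0% vs 13.2% | 4.55 | 3.37 |
| 0.4 | 0.50 | 0.5 | 0 | 3.0% vs 4.4% | 5.25 | 4.98 |
| 0.4 | 0.25 | 1 | 0 | 6.0% vs 8.8% | 4.55 | 4.65 |
| 0.4 | 0.50 | 0.5 | 0.2 | 20.0% vs 20.0% | 5.25 | 5.775 |
| 0.4 | 0.50 | 1 | 0.2 | 23.0% vs 24.4% | 5.25 | 5.48 |

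Across these cases the complete-case error runs from about −1.2 to +0.5 points, and its sign changes.

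**The case against.** The strongest reply is that the plan does provide for this group. Section XII commits the team to attempting consent in the manner used for NO patients, and the documents nowhere fix when that happens. Provider confirmation can come while the patient is still in the ED, and where no vaccine is on hand non-receipt is known at once. All of this stands. It means that some willing patients may be lost, not that all of them are. It does not remove the asymmetry, because YES patients alone must wait for a later fact.

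A reader might infer that the loss is heavier in the intervention arm and pulls the Aim IV effect towards zero. The documents do not support that. It needs the hypothesised rise in acceptance together with similar ED delivery in both arms. It also needs near-complete follow-up of NO patients, whose consent is optional and uncompensated and who are more numerous in control (about 548 vs 503). With 20% of them missing and half of the undosed YES patients lost, missingness is equal by arm and the bias is upward. A larger attenuation, to 3.85 points (0.1710 − 0.1325), appears if lost patients are counted as unvaccinated, but the plan classes patients with neither source as Indeterminate.

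A reader might also infer that the written-consent sentence forbids the next-day EHR check. That sentence sits in the month-1 section and refers to the follow-up techniques described there, so it can be read as limited to them. Similarly, the Section XIV bullet that names only non-accepters is out of line with the end of Section XII but does not cancel it. Both need a clarifying edit and no more.

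**Conclusion.** The point holds as a gap in the consent schedule for a primary outcome. Written consent from YES patients depends on a fact that may be known only after they have left, and an unsigned, undosed patient has no permitted route to a month-1 outcome. The group exposed is the undosed part of about 97 control and 142 intervention acceptors, at the planning rates of 15% and 22%. The number actually lost, the balance between arms and the direction of bias are not established: they rest on ED delivery, consent and later-uptake rates that the documents do not give. The change is worth making because it is cheap and the outcomes cannot be recovered afterwards.

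**What to change.** - **Section XII:** ask every participant, YES or NO, for the existing written follow-up consent and HIPAA form at the end of the second survey, before ED vaccination status is known, with the same script in both arms. The request follows the acceptance question, so it cannot alter the Aim III answer already given.
- **Section XIV:** amend the ascertainment bullet so that month-1 record review and calls cover everyone who consented and has no confirmed ED dose.
- **Sections XI and XIV and the 28 to 32 Day Follow-Up text:** reconcile the next-day EHR check, made on verbal permission, with the written-consent sentence. Either state that the sentence covers only month-1 methods, or let the new consent cover both.
- **Reporting:** tabulate Indeterminate outcomes by arm and by YES/NO answer, so that any imbalance can be seen.

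The cost is an amendment to the manual and the consent script. The form already exists, and at most about 239 YES patients (97 + 142) are affected, many of whom would be asked anyway. The downside is that some patients will sign a form that proves unnecessary because they are vaccinated in the ED.

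### Blinding of the 28 to 32 day follow-up rests on staffing alone, while the described workflow runs through a form cited for study arm and platform delivery

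*Combined protocol and SAP*

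**What the plan says.** All references are to the combined protocol and SAP.

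- **The commitment.** The section 28 to 32 Day Follow-Up for Ascertainment of Primary Outcomes says "The CRC who conducts this EHR and phone follow-up will be blinded" to study group.
- **The mechanism.** The only means given is that "a separate CRC who does not recruit at that site will conduct this phone follow-up".
- **Finding patients who are due.** The same section says "CRCs will review Master Data Flow daily (workdays) to determine which subjects have reached the 28-day follow-up time period".
- **Entering results.** Within the instructions for the phone call, it adds: "CRCs will enter follow up data on both the Master Data Flow and Follow up spreadsheets".
- **What the logs hold.** Data Recording and Entry describes a running log, "recording on REDCap forms the following data for all patients approached: study date, study arm", followed by other items that include whether the messaging platforms were delivered. It closes the list with "See Enrollment Log and Master Data Flow" and does not say which form holds which field.
- **When the form is completed.** The Intervention Blocks section has the Master Data Flow completed after each enrolment. The Non-Intervention Blocks section has the screening and enrollment log filled in first, and the coordinator moves to the Master Data Flow only for patients who agree to the survey.
- **Contact data.** Medical record and telephone numbers come from a separate Follow up sheet.

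**The concern.** A statement that an assessor is blinded is only as good as the control over what the assessor can see. Here the plan separates people but says nothing about separating data. If the follow-up coordinator opens the Master Data Flow and it shows arm or platform delivery, the person who ascertains much of a primary outcome knows the allocation.

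The outcome leaves room for that knowledge to act. A phone self-report of vaccination is enough for a Yes. A negative record review with an incomplete call is scored No. More effort to reach or question patients in one arm would therefore turn directly into a difference in recorded uptake. A report of the trial would also claim assessor blinding that its own procedures did not protect.

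**Working it through.** **1. The passages side by side**

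| Question | What the text gives | What it leaves open |
|---|---|---|
| Is the follow-up coordinator blinded? | Yes, by using someone who does not recruit at that site | Any limit on which forms or fields that person sees |
| Who reviews the Master Data Flow for due patients? | Coordinators in general | Whether this includes the blinded one |
| Who writes follow-up results into it? | Coordinators, in the instructions for the phone call | Whether entry is through a restricted view; REDCap links are mentioned without detail |
| Where are arm and delivery recorded? | Enrollment Log and Master Data Flow, cited jointly | Which field is on which form |
| Is access restricted anywhere? | The Data management plan keeps identifiers apart from study data | This protects confidentiality; it does not hide arm |

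The data-entry sentence is the firmest link. It sits in the step where the blinded coordinator phones the patient, so it most naturally applies to that coordinator.

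Arm is listed as recorded for everyone approached, so it should be on the Enrollment Log; whether it is repeated on the Master Data Flow is not stated. Platform delivery happens after enrolment, and the Master Data Flow is the form completed for enrolled patients, so delivery plausibly sits there. A record of a delivered platform discloses the intervention arm without any arm field.

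**2. How far one entry reaches**

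Under Randomization, allocation is by one-week period within site. One visible arm entry, or one entry showing a platform delivered, reveals the arm of every patient enrolled at that site in that week.

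**3. The plan's own figure**

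Inputs from Sample Size Considerations: control uptake 15%, difference 7 points (so 22%), alpha 0.05, power 0.90. The sidedness of alpha is not stated; two-sided reproduces the figure.

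n = [1.960 × √(2 × 0.185 × 0.815) + 1.282 × √(0.15 × 0.85 + 0.22 × 0.78)]² / 0.07² = [1.960 × 0.5491 + 1.282 × 0.5469]² / 0.0049 = 644.6, rounded up to 645 per arm, or 1,290 in total. This matches the plan.

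**4. Illustration of what unequal ascertainment could do**

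Assumptions, not from the documents: no true effect, true uptake of 15% in both arms, and unequal follow-up that adds b to recorded uptake in one arm. With 645 per arm and a two-sided 5% test, the rejection probability is

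P = 1 − Φ[(1.960 × SE0 − b)/SE1] + Φ[(−1.960 × SE0 − b)/SE1],

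where SE0 is the pooled and SE1 the unpooled standard error for 15% against 15% + b. For b = 0.01 both are 0.02015, so P = 1 − Φ(1.464) + Φ(−2.456) = 0.0716 + 0.0070 = 0.079.

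| Excess b | Extra Yes records among 645 | False-positive rate |
|---|---|---|
| 0 | 0 | 5.0% |
| 1 point | 6.5 | 7.9% |
| 1.5 points | 9.7 | 11.5% |
| 2 points | 12.9 | 16.5% |
| 2.5 points | 16.1 | 22.9% |

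The formula treats patients as independent and ignores clustering by site and week.

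**The case against.** The best defence is that the protocol already made the important choice, a separate and blinded follow-up coordinator, and that only an access detail is missing. Several parts of that defence stand.

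- **A reader might infer that the blinding fails outright.** The documents do not support this. Arm is not assigned to the Master Data Flow, the forms are not reproduced, and REDCap links might open a limited view.
- **A reader might infer that the blinded coordinator must do the daily review.** That task is given to coordinators generally. Another person could do it and pass on the Follow up sheet.
- **A reader might infer that index date plus the weekly calendar discloses arm.** That needs sight of the calendar for that site, and nothing gives the follow-up coordinator this. Knowing the arm at one's own site says little about another: with a 3 to 2 split of five sites, 4 of the 10 site pairs share an arm in any week (3 + 1 pairs).
- **A reader might extend the point to the whole uptake outcome.** Blinding is claimed only for the 28 to 32 day follow-up. Receipt in the ED is confirmed with providers or by next-day record review, with no blinding claimed.
- **Discretion is limited.** The question and the call schedule are fixed, and a vaccination found in the record ends the search. Patients also know what messaging they received, so bias in their own answers would survive any fix.

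What does not stand is that the gap is mere missing detail. The text directs follow-up data into a form cited for arm and delivery and describes no restriction. Following it as written would probably show arm or delivery to the assessor.

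**Conclusion.** The point holds in a limited form. For the 28 to 32 day record review and phone follow-up, the stated blinding is not ensured and is apparently contradicted by the procedures in the same section. This rests on two readings: that the data-entry sentence covers the blinded coordinator, and that the Master Data Flow shows arm or platform delivery. Both are the natural reading, and neither is proved.

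The size of any bias is unknown. The range of about 8% to 23% for the false-positive rate depends on an assumed excess of 1 to 2.5 points, 15% true uptake in both arms, 645 patients per arm and no clustering. It shows that a handful of differently ascertained patients would matter; it does not estimate what will happen. The sample size is not in dispute. The sponsor should correct this, because the outcome is primary and partly self-reported and the remedy is cheap.

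**What to change.** In the 28 to 32 Day Follow-Up section:

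1. State which form holds study arm and which holds platform delivery.
2. Give the follow-up coordinator a REDCap role or worklist that shows only study ID, index or due date, consent scope (record review, phone or both) and the contact link.
3. Hide the arm, platform-delivery and Second Survey version fields and the allocation calendar from that role. The survey version matters because the two arms use different versions.
4. Have follow-up results entered only on the Follow up form and linked to the Master Data Flow by study ID.
5. Assign any review of the full Master Data Flow to someone other than the follow-up coordinator.

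In Data Recording and Entry, add a matching sentence on access. If the forms already hide these fields, a sentence saying so is enough.

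The cost is a small REDCap configuration task and an edited paragraph. The separate coordinator and REDCap are already planned, so no staff are added and neither the sample size nor the analysis changes.

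### Patients with a negative EHR and no completed phone call are scored as definitely unvaccinated, so doses given outside the ED can be undercounted, with a bias on uptake whose direction and size the plan leaves open

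*Combined protocol and SAP*

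**What the plan says.** Under Primary Outcomes and Ascertainment (section XIV), the Aim IV primary outcome is receipt of a COVID-19 "vaccine (at any vaccination location) within 28 to 32 days after their index ED visit". The Primary Analysis section names uptake as one of two primary outcomes and analyses it by mixed logistic regression.

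The 28 to 32 Day Follow-Up section sets the order of checks for subjects who gave written consent. The EHR comes first, and then: "If there is no record of vaccination in the EHR, the CRC will proceed with a phone call to the study subject". After three unanswered calls, a message and a week without a call back, "the phone follow up will be considered as incomplete".

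The final scheme for Aim IV then classifies as follows:
- Yes, by any of three routes. One is "Confirmed receipt of Covid vaccine during index ED visit", which does not depend on the one-month follow-up.
- No, when all sources are negative. For subjects without an in-ED dose, "these 2 scenarios will also qualify as Covid vaccine not received", and the first of the two is "Did not received Covid vaccine on EHR review but unable to complete phone follow-up".
- Indeterminate, only when both sources fail: "Unable to review EHR and Unable to contact subject via phone call".

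Section XII adds: "Patients may agree to a phone call and not the EHR review, or vice versa". The plan does not say whether EHR-only consenters count as unable to complete phone follow-up. It gives no missing-data method, bounds or sensitivity analysis for phone-incomplete or Indeterminate subjects.

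**The concern.** The follow-up procedure treats a negative EHR as inconclusive, and the scoring scheme treats the same record as conclusive once the calls fail. A dose from a pharmacy or community site that never reaches the hospital record is then counted as no dose.

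The error depends on where the dose was given. In-ED doses are confirmed with the provider or by next-day EHR review, so they are essentially all counted. Outside doses count only if the EHR shows them or the patient answers. Outside doses are to be expected, because section XIII offers community locations to patients who decline in the ED. The intervention aims at acceptance in the ED that day, so it could change where doses are given as well as how many. If it does, the misclassification differs by arm and need not pull towards no effect. At stake are the estimate, the power and possibly the error rate for a primary outcome.

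**Working it through.** **Inputs from the plan** (Sample Size Considerations): control uptake 15%, difference of interest 7 points, alpha 0.05, power 0.9, 645 per arm, individual-randomisation formula.

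**Reproducing the plan's figure.** Two-sided, pooled variance under the null, no continuity correction:

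n = [1.96·√(2·0.185·0.815) + 1.2816·√(0.15·0.85 + 0.22·0.78)]² / 0.07² = 644.6, so 645 per arm. This matches exactly, and power at 645 is 0.900.

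**Inputs the plan does not give** (assumed, shown as ranges): EHR capture of outside doses (e), phone reach among EHR-negative subjects (r), and the ED/community split. Detection of an outside dose is s = e + (1 − e)r. With e from 0.3 to 0.9 and r from 0.4 to 0.8, s runs from 0.3 + 0.7·0.4 = 0.58 to 0.9 + 0.1·0.8 = 0.98, so 2% to 42% of outside doses would be scored No. I take s as equal in both arms, everyone as consenting to both follow-up routes, and no clustering (as in the plan's own formula).

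**Bias formula.** Observed uptake = ED doses + s × community doses. Hence

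bias in the risk difference = −(1 − s) × (community rate, intervention − community rate, control).

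The sign depends on community doses alone, not on in-ED doses.

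**Case 1: no true effect, some doses relocated into the ED.** Control 5% ED + 10% community; total 15% in both arms. Rejection = 1 − Φ(1.96 − d/SE) + Φ(−1.96 − d/SE), with unpooled SE at 645 per arm.

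| s | points moved | control observed | intervention observed | d | rejection |
|---|---|---|---|---|---|
| 0.65 | 2 | 11.50% | 12.20% | +0.70 | 6.8% |
| 0.65 | 3 | 11.50% | 12.55% | +1.05 | 8.9% |
| 0.85 | 2 | 13.50% | 13.80% | +0.30 | 5.3% |
| 0.85 | 3 | 13.50% | 13.95% | +0.45 | 5.6% |

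Larger figures need stronger assumptions:
- Half of all community doses moved (5 points) at s = 0.58: 10.8% v 12.9%, rejection 21.5%.
- A 20% total in both arms, with 14 v 8 points in the ED: at s = 0.65, 0.14 + 0.06·0.65 = 17.9% v 0.08 + 0.12·0.65 = 15.8%, rejection 17%. At s = 0.85, 19.1% v 18.2%, rejection 7%.

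**Case 2: true 15% v 22%, all gain in the ED (community 10% in both arms).** The difference stays at 7 points. The true odds ratio is (0.22/0.78)/(0.15/0.85) = 1.60. At s = 0.7 it becomes (0.19/0.81)/(0.12/0.88) = 1.72; at s = 0.9, 1.63; at s = 0.58, 1.79.

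**Case 3: true 15% v 22%, all gain in the community (10% v 17%).** The observed difference is 7s points: 6.3 at s = 0.9, 4.9 at 0.7, 4.1 at 0.58. Power is 0.85, 0.71 and 0.59.

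**Case 4: true 15% v 22%, same location mix in both arms, s = 0.7.** With half of doses outside the ED, both rates are multiplied by 0.85: 12.8% v 18.7%, power 0.84. With all doses outside: 10.5% v 15.4%, power 0.75.

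**The case against.** A reader might infer that the rule manufactures a benefit for the intervention. The documents do not support that. A false benefit on the risk difference needs fewer community doses in the intervention arm, that is, relocation. Nothing in the plan predicts relocation without net gain, and messaging that also prompts community vaccination would bias the comparison against the intervention. The 17% error rate uses a 20% baseline instead of the plan's 15% and moves 6 points, 30% of all doses, with no net gain. It is a corner case.

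The design also limits arm-dependent detection. The follow-up CRC is blinded and separate from recruitment, the call schedule is the same for everyone, and the acceptance question, provider notification and community information carry no arm distinction. These features stand. They reduce assessor bias, but they cannot recover a dose that neither source recorded.

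EHR capture is unknown, not shown to be poor. The form records where an EHR-listed dose was given, so some outside doses are expected to appear. At 95% detection even the corner case falls to +0.3 points and 5.2% rejection.

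A reader might also infer that imputation should replace the current rule. That goes too far. A negative EHR is a real observation, and imputation assumes that answering the phone is unrelated to vaccination given the covariates. For illustration, assume 5% ED + 10% community, EHR capture 60%, and phone reach 80% in vaccinated and 60% in unvaccinated EHR-negative subjects. The rule gives 5 + 6 + 3.2 = 14.2%. Imputation from those reached adds 3.2/(3.2 + 51) × (0.8 + 34) = 2.1, giving 16.3%. The truth is 15%, so neither is unbiased. This stands, and it is why the two should be reported together.

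**Conclusion.** The inconsistency is real, and nothing elsewhere in the plan corrects it: a record that the follow-up procedure calls incomplete becomes a definite negative on a primary outcome that counts doses anywhere. Unless the EHR captures all outside doses, uptake is undercounted.

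The effect on the treatment comparison is conditional:
- Fewer community doses in the intervention arm: the difference favours the intervention.
- Equal community doses: the difference is unbiased, but the odds ratio estimated by the logistic model is inflated when in-ED doses differ.
- More community doses in the intervention arm: effect and power shrink.

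Under the 15% baseline and moderate relocation, the false-positive rate is about 5% to 9%, a modest excess over 5%. The loss of power in the other direction can be larger. All of these sizes rest on assumed capture, reach and location split, so the documents establish neither a material false benefit nor its absence. The point merits a change because the plan offers no way to see whether the uptake conclusion depends on the scoring rule.

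**What to change.** - Record EHR-negative, phone-incomplete subjects without an in-ED dose as a separate category. Say explicitly that it includes those who consented to EHR review only.
- Keep the current incomplete-means-No analysis. Beside it, prespecify multiple imputation for this category, conditional on EHR-negative status, arm, site, week, Second Survey acceptance and FIRST SURVEY characteristics, together with best-case and worst-case bounds by arm.
- Require both analyses and the bounds to be reported, and do not describe an uptake effect as robust unless it holds under both the current rule and the imputation.
- Tabulate ascertainment route (ED, EHR, phone, incomplete) by arm, and state whether the site EHRs draw on an immunisation registry.

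The cost is SAP wording, one imputation model and one table; the ascertainment routes are already recorded, so no new data are collected. The imputed estimate will have a somewhat wider interval and rests on an untestable missing-at-random assumption.
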